Jane scored a 4 on the AUDIT-C and a 2 on the MINI on her PRO. After a page was received (please see page XXX for more information on pages), ARCH-IRA study staff approaches Jane in clinic. Jane decided to postpone enrollment until her next clinic visit in 6 months. Jane will need to complete a new PRO at her clinic visit in 6 months.

- If she does not complete a PRO during her clinic visit, the ARCH-IRA study staff can still approach for enrollment into ARCH-IRA.
- If she does complete a PRO during her clinic visit and she her new AUDIT-C score is a 2, then Jane is no longer considered eligible for ARCH-IRA and study staff will not approach.
- If she does complete a PRO during her clinic visit and she her new AUDIT-C score is a 6 and study staff received a new Peedy page, then Jane can be approached again for enrollment.

III. Randomization

Randomization will be programmed into the CNICS PRO platform. Controls will not be approached for any study activity. Study staff will receive pages for only intervention participants. Randomization process occurs before the consenting takes place. It is a 5:1 assignment for intervention and controls. Intervention vs. control status will be tracked in the PRO platform.

IV. Peedy alerts

If a patient meets the eligibility criteria (page XXX) for ARCH-IRA, a Peedy alert is generated through the CNICS PRO platform, which is developed and run by the UW team. A Peedy alert can come through as a page and/or an email to the appropriate study staff. Each page and/or email sent will include the following: patient's ticket number (ticket generated through CNICS, valid only 48 hours); the PRO session number; and the version of Peedy the patient is eligible for (please refer to page XXX for more information on the different versions of Peedy).

A. UAB

Study staff will approach eligible patients in clinic after receiving the Peedy alert. Staff will follow the ARCH-IRA recruitment script (Appendix 3) when approaching in clinic.

B. UW

The UW will use the same script and approach as UAB and will document status including refusals and reasons in the tracking log/PRO platform. (**Note at UW: there is likely not a handoff between two staff members as described above for UAB but instead the same staff member will proceed with the consent process if the participant is willing.)

C. UCSD

TBD

D. JHU

TBD

V. Enrollment and Informed Consent

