Informed consent will be obtained from the patient prior to participation in any study-related activities. Only trained study personnel with appropriate Human Subjects training will review and explain the consent form and study participation with potential enrollees. Study staff will ensure that the participant understands that their consent is voluntary to avoid coercion. Patients will be approached in private rooms or designated study space for informed consent procedures by trained study staff. ARCH-IRA study staff at all sites will follow their site's IRB guidance for obtaining informed consent.

VI. Interventions

A. Peedy video versions

i. Visit 1

For visit 1, participants can be eligible for Peedy Prime or Peedy Pharma. Peedy Prime is for participants who report heavy or binge drinking on the AUDIT-C but do not meet Alcohol Use Disorder (AUD) criteria based on the MINI. Peedy Pharmacotherapy (aka Peedy Pharma) is for participants who meet criteria for AUD at visit 1 or have a PHQ5 > 5 or PHQ9 \geq 10. A Peedy satisfaction survey will automatically follow all of the video versions.

ii. Visit 2

For visit 2, participants can be eligible for Peedy Prize, Peedy Problem, or Peedy Adherence. Peedy Prize is for participants who have reduced their drinking from Visit 1 to low-risk limits. Peedy Problem is for participants who received Peedy Prime on Visit 1 and continue to report risky drinking. Peedy Adherence is for participants who received Peedy Pharma during Visit 1 and are still reporting risky drinking. A Peedy satisfaction survey will automatically follow all of the video versions.

B. Text Messages

During visit 1, all participants are eligible to receive text messages that reinforce content from the intervention. Please explain that the texts do not contain any personal information and none of the content can be traced back to the participant, but the texts do suggest ways to cut down on alcohol.

For participants who opt-in to receive the text messages, study staff will refer to steps #6-10 under "Logging into Peedy" on page XX. It is critical to enter the correct phone number to ensure that participants receive the texts and guarantee that the intervention is linked to the correct cellphone.

For participants who do not opt-in to receive text messages, study staff should ask for a reason(s) as to why and document that reason in the local study log. Possible reasons for participants to refuse text messages:

- I don't have a cell phone

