- I don't want to receive any text messages
- I don't want to use my data/minutes
- I am concerned text messages will be seen by others
- I don't think text messages about my alcohol will help me with my drinking
- I don't like to receive text messages
- I don't carry my phone with me and would not get texts on time
- I don't believe I need help with my drinking
- Other: _____

C. CBT4CBT

i. Visit 1

During visit 1, participants who have PHQ5 ≥ 5 and/or PHQ9 ≥ 10 or have AUD on MINI would also would become eligible to receive CBT4CBT ([Appendix 1 Algorithm 1](#)). A unique CBT4CBT study ID would be assigned for each participant through CBT4CBT database. Study staff would be able to track each participant on their completion of CBT4CBT modules.

Patient care coordinator (PCC) and/or study staff will introduce CBT4CBT with participants (please see example introduction script below). The study staff and/or PCC will show the participant how to login to CB4CBT modules and provide each participant a unique username and password. The study staff or PCC will also provide a sheet with the link and login information, worksheets and some instructions to the participant ([Appendix XX](#)). The study staff and/or PCC will follow-up by phone with the participants after about a week to check in and see if they have any issues with completing the CBT4CBT modules. Study staff should use an IRB-approved (if applicable) phone script when calling participants. (*Note: please check with your site's IRB to see if you need to have an IRB-approved phone script or not.)

Example CBT4CBT introduction script:

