Enter user name: uabmcD0

Password: BU6007

Click Reports, select start and end date and click 'generate'.

D. Alcohol Pharmacotherapy (APT)

During visit 1, participants who have scored AUD on MINI would become eligible to receive Alcohol Pharmacotherapy (APT).

Providers/PCC/study staff can call/page [name]/ [name] in case they have questions on medications.

Information for [name]:

- ✓ [contact]
- ✓ [contact]
- ✓ Email: [contact]

Information for [name]:

- ✓ [contact]
- ✓ [contact]
- ✓ Email: [contact]

In instances where you cannot reach them by phone and need to leave a VM.

VM to leave: *Hi this is 'XYZ', I have a question on ARCH IRA participant who is in the clinic/ or not in the clinic (use as appropriate). Please call back at 'phone number'.*

Paging instructions:

- Go to <https://www.paging.uab.edu/>
- Enter the last 4 digits of the pager number or name in the box and click search. You will see name and pager number that pops up.
- Click the pager number which is bold and green and a screen will come up saying enter your message and send button. You can only enter 80 characters for message.
- Enter message and click hit send.
- Message to send: *Question on ARCH IRA participant. Call back on 'phone number'.*

i. UAB

Study staff/PCC will use the APT algorithm ([Appendix 1 Algorithm 2](#)) and the EMR to determine which medication to recommend to the provider. Study staff/PCC will communicate with participant's provider in clinic and/or send a message through the EMR and recommend a drug from the APT list. These recommendations will be done based on APT algorithm plus consultation with PI ([name]) of the study/addiction specialist ([name] [name]) on case-

by-case basis via email or phone communication. Template scripts of these recommendations can be found in **Appendix XX**.

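### Do the different Visit 1 PHQ5 cut-offs for the Peedy Pharma video and for CBT4CBT make the treatment algorithm wrong as written?

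*Protocol*

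**What the plan says.** Section VI.A.i states that at Visit 1 "participants can be eligible for Peedy Prime or Peedy Pharma". The first of these goes to "participants who report heavy or binge drinking on the AUDIT-C but do not meet Alcohol Use Disorder (AUD) criteria based on the MINI". The second goes to "participants who meet criteria for AUD at visit 1 or have a PHQ5 > 5", or to those with PHQ9 at or above 10.

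Section VI.C.i makes CBT4CBT available at the same visit to "participants who have PHQ5 ≥ 5 and/or PHQ9 ≥ 10 or have AUD on MINI", and cites Appendix 1 Algorithm 1. Of that appendix only the title can be read here; the flow chart is not shown.

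The Visit 1 video determines the Visit 2 video when risky drinking persists (section VI.A.ii). On the Prime branch, "Peedy Problem is for participants who received Peedy Prime on Visit 1 and continue to report risky drinking". On the Pharma branch the rule reads "Peedy Adherence is for participants who received Peedy Pharma during Visit 1 and are still reporting risky drinking".

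Section VI.D ties eligibility for alcohol pharmacotherapy to AUD on the MINI and mentions no PHQ score. Section IV says the platform alert tells staff which Peedy version the patient qualifies for. In section VI.F, staff choose the video package at step 3 and record CBT eligibility on its own at step 17.

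**The concern.** Two rules for the same visit share the AUD trigger and the PHQ9 trigger and differ only in whether a PHQ5 of exactly 5 counts. That looks like a typing error in one of them. PHQ5 appears nowhere else in the readable text, so nothing there shows which sign was meant.

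There is a second oddity. The Prime definition carries no PHQ condition. A heavy or binge drinker without AUD who meets a PHQ trigger therefore fits the wording of both Prime and Pharma, and section VI.A states no order of precedence.

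The trial tests algorithm-guided treatment, so these cut-offs are part of the intervention. If sites read them differently, similar participants would see different videos at Visit 1, and at Visit 2 if risky drinking continued. The pointer that should help staff is unfilled: "please refer to page XXX for more information on the different versions of Peedy".

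**Working it through.** No sample size, power or error rate is involved, so the check is an enumeration of the printed rules.

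**Inputs** (sections VI.A.i and VI.C.i)
- Prime = heavy or binge drinking on AUDIT-C, and no AUD.
- Pharma = AUD, or PHQ5 > 5, or PHQ9 ≥ 10.
- CBT4CBT = AUD, or PHQ5 ≥ 5, or PHQ9 ≥ 10.

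**Profiles.** AUD (2 levels) × PHQ5 below, at or above 5 (3 levels) × PHQ9 below 10 or not (2 levels) = 12. Heavy or binge drinking is taken as present. The comparison of Pharma with CBT4CBT does not depend on this, because neither rule contains a drinking term.

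The six profiles without AUD, as printed:

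| PHQ5 | PHQ9 | Prime | Pharma | CBT4CBT |
|---|---|---|---|---|
| < 5 | < 10 | yes | no | no |
| < 5 | ≥ 10 | yes | yes | yes |
| = 5 | < 10 | yes | no | **yes** |
| = 5 | ≥ 10 | yes | yes | yes |
| > 5 | < 10 | yes | yes | yes |
| > 5 | ≥ 10 | yes | yes | yes |

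In all six AUD profiles Prime is no and both Pharma and CBT4CBT are yes.

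**Results**
- Pharma and CBT4CBT agree in 11 of 12 profiles and differ in 1 (third row).
- With the inclusive sign in both places, or the strict sign in both, they differ in 0.
- Prime and Pharma overlap in 4 profiles as printed, 4 with both signs strict and 5 with both inclusive. The overlap is therefore a separate matter from the sign.

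**What happens in the third row.** The participant fits one video, Prime, and is also eligible for CBT4CBT. Steps 3 and 17 of section VI.F allow that combination. Persistent risky drinking then leads to Peedy Problem at Visit 2. No step is undefined.

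**What happens in the four overlap rows.** If Prime prevailed, the PHQ triggers written into the Pharma rule would do nothing for heavy drinkers without AUD. Reading those triggers as having a purpose gives Pharma. Staff also receive one version from the alert and need not derive it.

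**What the sign cannot reach.** Section III places the 5:1 randomisation in the platform before consent, and controls are not approached, so video routing happens only within the intervention arm. Trial eligibility in section I rests on AUDIT-C, AUDIT and MINI; its only PHQ element is the suicidal-ideation item of PHQ9. Section VI.D does not use PHQ5. Section VII logs which Visit 1 and Visit 2 videos were viewed.

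**The case for a change.** The best argument for a change is that the routing is the intervention, that it belongs in the protocol and not in an analysis plan, and that a correction would cost a few words. In the machine-read text the neighbouring PHQ9 sign came through as raw code for the inclusive sign, while the PHQ5 sign came through as a plain strict sign. This suggests that the source has two different characters. Aligning the PHQ5 signs would still leave the Prime and Pharma wording overlapping.

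Part of this stands. The printed signs differ, the readable text gives no reason, and section VI.A could have stated precedence outright.

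It does not establish an error. That sentence visibly suffered in conversion, and an inclusive sign can lose its lower stroke, so the strict sign is likely but not proven. If it is genuine, a different threshold for a video and for a web programme may be intended. The flow chart that could settle both matters is not shown, so silence in the readable text is not silence in the plan. The unfilled page pointer is clerical, since the video rules it should lead to stand in section VI.A.

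The protocol does not state the PHQ5 score range. If the maximum were 5 (an assumption), the strict trigger could never be met, but the two rules would still differ only at a score of exactly 5.

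**Conclusion.** The observation is accurate, but no change to the plan follows. As printed, the rules differ for 1 of 12 logical profiles, and participants in that profile still have a defined, deliverable route. The effect is on which video version some intervention participants see. It does not touch allocation, trial eligibility or eligibility for medication, and no bias or altered conclusion has been shown. The number of participants affected cannot be obtained from the document.

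This rests on three assumptions: the platform applies one rule uniformly across sites; the alert sends a single version, as section IV implies; and the Algorithm 1 flow chart does not contradict sections VI.A and VI.C. If the flow chart or the source file showed a different cut-off, those places would have to be reconciled. Which cut-off applies is for the clinical team, and nothing here favours either.

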If APT is prescribed to the participant, study staff/PCC will communicate with participant about the side effects of the recommended drug (described in Appendix 2 under medication list) and make sure that the participant understands to call study staff/PCC and clinical care team in case s/he experiences any side effects. In addition, study staff/PCC will follow up with participants in one week to see how they are doing on their medication. Attempts will be made up to one month following receipt of medication. Study staff/PCC will call twice per week in attempting to reach the participant. If participant reports a side effect, the study staff/PCC will inform the participant's clinical care team using message center in the Cerner. The provider will determine the course of action to be taken (e.g., continue, reduce dose, and discontinue medication). [name]/ [name] will be available for provider to consult about medication.

ii. UW

A similar set of procedures will be used for most of these steps at the UW.

Providers will receive a notification for patients eligible for APT:

XX is participating in the ARCH-IRA study and reported at-risk alcohol use on the clinical assessment. Based on XX's risk, he is eligible and would likely benefit from Alcohol Pharmacotherapy (APT). Naltrexone is most often recommended for APT unless the patient has acute hepatitis or liver failure (LFTs>5x ULN) or is currently using prescribed or illicit opioids. The dose of naltrexone is 50 mg PO per day. We have attached an APT medication algorithm and list of medications and doses for your information. We hope this information is useful to you and that you consider whether prescribing APT would be of benefit to George.

At UW, this message can be sent through Epic with algorithm attached or printed and handed directly to provider. The assessment of appropriateness of specific APT choices based on LFTs or opiate use will be assessed by and at the discretion of the patient provider. The PCC will contact participants as above and address issues with participant regarding access, receipt of, and other issues with APT but side effects will be deferred to clinical staff.

iii. UCSD

TBD

iv. JHU

TBD

E. Dried Blood Spots

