- Approached refused, not okay to re-approach
- Consented

After selecting the event that best fits your situation, click “Add New Event” in order for it to save.

After consenting a participant for ARCH-IRA and after updating the Protocol History to show “Consented,” a new drop-down will appear for Visit 1. After the participant either completes all or some of Visit 1 or refuses to complete Visit 1, you will update the “Protocol History” with the following options:

Visit 1 drop-down options:

- Withdrawn
- Viewed video 1 Peedy Prime
- Viewed video 1 Peedy Pharma
- Refused video 1
- Refused CBT4CBT
- Refused Pharmacotherapy
- Completed Visit 1

Visit 2 drop-down options:

- Withdrawn
- Eligible – not approached (Video 2)

[figure not shown]
Postpone Video 2
Viewed video 2 Peedy Adherence
Viewed video 2 Peedy Problem
Viewed video 2 Peedy Prize
Refused video 2
Refused CBT4CBT
Refused Pharmacotherapy
Completed Visit 2

APPENDIX 1

Algorithm 1. Overall study algorithm

Algorithm 2. APT algorithm

APPENDIX 2

APT –Medication List

Name	Method	Dosage	Side Effects
Campral (acamprosate)	Tablet	Two 333mg tablets 3x/day with or without food. Some patients may require a lower dose.	
Common side effects: abdominal pain, appetite change, change in sexual desire, diarrhea, dry mouth, gas, itchy skin, nausea, nervousness, prickling or tingling sensation, skin rash, trouble sleeping, vomiting, weakness, weight gain or loss
 
More serious side effects: chest pain, joint pain, pounding or fast heartbeat, symptoms of depression, and thoughts or acts of self-harm
 
Other: Does not help with alcohol withdrawal

Disulfiram (antabuse)	Tablet	250mg or 500mg 2 or 3x/day	
Common side effects: skin rash, mild headaches, metallic taste, mild weakness, dizziness, swollen tongue
 
More serious side effects: allergic reactions (swelling of lips, face) and hives, shortness of breath, seizure, tiredness, yellowing of skin or eyes, dark urine, appetite changes, dizziness, vomiting, weakness, severe diarrhea
 
Other: Produces unpleasant effects if you drink alcohol while taking it

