Vivitrol (PO naltrexone)	Tablet	50 mg 1x/day with food	
Common side effects: nausea, vomiting, stomach pain, diarrhea, constipation, loss of appetite, headache, dizziness, anxiety, nervousness, irritability, tearfulness, difficulty sleeping, increased or decreased energy, drowsiness, muscle or joint pain, rash
 
More serious side effects: confusion, hallucinations, blurred vision, severe vomiting and/or diarrhea

Opioid list as prescribed in Cerner at UAB

Opiates
acetaminophen/butalbital/caffeine/codeine
acetaminophen-codeine
acetaminophen-HYDROcodone
acetaminophen-oxycodone
acetaminophen-tramadol
APAP/butalbital/caffeine/codeine
APAP/caffeine/dihydrocodeine
aspirin/butalbital/caffeine/codeine
aspirin-oxycodone
bupivacaine-fentanyl 200 mL
bupivacaine-fentanyl 250 mL
bupivacaine-HYDROMorphone 250 mL
buprenorphine
buprenorphine-naloxone
butorphanol
chlorpheniramine/hydrocodone/phenylephri
chlorpheniramine/hydrocodone/phenylephrine
chlorpheniramine-hydrocodone
codeine
codeine/guaifenesin/PSE
codeine/guaiFENesin/pseudoephedrine
codeine/phenylephrine/promethazine
codeine-guaifenesin
codeine-promethazine
dexbrompheniramine/hydrocodone/phenyleph
dexbrompheniramine/hydrocodone/phenylephrine
dihydrocodeine/guaiFENesin/phenylephrine
diphenhydramine/hydrocodone/phenylephrine
fentanyl
fentanyl 1
fentanyl 1,000 mcg [0.5 mcg/kg/hr] + dex
fentaNYL 2
fentaNYL 2,500 mcg [100 mcg/hr] + empty
fentaNYL 2,500 mcg [100 mcg/hr] + empty sterile container for IV fluids 50 mL
fentanyl 2,500 mcg [200 mcg/hr] + empty
fentaNYL 2,500 mcg [25 mcg/hr] + empty s
fentaNYL 2,500 mcg [25 mcg/hr] + empty sterile container for IV fluids 50 mL

fentaNYL 2,500 mcg [50 mcg/hr] + empty sterile container for IV fluids 50 mL
fentanyl 2,500 mcg [75 mcg/hr] + empty s
fentanyl 2,500 mcg [75 mcg/hr] + empty sterile container for IV fluids 50 mL
fentanyl 2500 mcg + empty sterile contai
fentaNYL 5
fentaNYL 5,000 mcg [1 mcg/hr] + empty st
fentaNYL 5,000 mcg [1 mcg/hr] + empty sterile container for IV fluids 100 mL
fentaNYL 5,000 mcg [10 mcg/hr] + empty sterile container for IV fluids 100 mL
fentaNYL 5,000 mcg [100 mcg/hr] + empty
fentaNYL 5,000 mcg [100 mcg/hr] + empty sterile container for IV fluids 100 mL
fentaNYL 5,000 mcg [150 mcg/hr] + empty
fentaNYL 5,000 mcg [150 mcg/hr] + empty sterile container for IV fluids 100 mL
fentaNYL 5,000 mcg [200 mcg/hr] + empty
fentaNYL 5,000 mcg [200 mcg/hr] + empty sterile container for IV fluids 100 mL
fentanyl 5,000 mcg [25 mcg/hr] + empty s

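### At UAB the only written step for staff who hear of an alcohol-pharmacotherapy side effect is a Cerner message, even when the effect is urgent

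*Protocol*

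**What the plan says.** Section VI.D.i sets out what happens at UAB once a drug is prescribed.

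- Staff or the PCC explain the side effects listed in Appendix 2 and "make sure that the participant understands to call study staff/PCC and clinical care team in case s/he experiences any side effects".
- They then make a check-in call: "study staff/PCC will follow up with participants in one week to see how they are doing on their medication". They try twice a week, for up to a month after the drug is received.
- If a side effect is reported to them, they inform the participant's "clinical care team using message center in the Cerner". The provider then decides what to do; the examples given are continuing, reducing the dose and stopping.

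Appendix 2 divides each drug's effects into common and more serious. The more serious entries include:

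- Acamprosate: "chest pain, joint pain, pounding or fast heartbeat, symptoms of depression, and thoughts or acts of self-harm".
- Disulfiram: "allergic reactions (swelling of lips, face) and hives, shortness of breath, seizure", followed by further items such as yellowing of the skin or eyes and dark urine.
- Naltrexone: "confusion, hallucinations, blurred vision, severe vomiting and/or diarrhea".

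The opening of section VI.D also lets providers, the PCC and study staff call or page two study contacts "in case they have questions on medications".

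**The concern.** The protocol sorts drug effects by seriousness in Appendix 2, but the staff rule in VI.D.i makes no use of that sorting. Dry mouth and a seizure follow the same written step.

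This matters because the design makes staff a likely first point of contact. They place the follow-up calls, and participants are told to ring them. The decision to stop a drug lies with the treating provider. If staff hear of an urgent effect first and do only what the protocol says, the provider learns of it when the message is opened. Lost time could matter for self-harm, chest pain, seizure or facial swelling.

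**Working it through.** The protocol states no figure on this point and none needs recomputing. The check is whether any other provision gives staff a different step for an urgent effect.

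1. **The relay sentence (VI.D.i).** It applies to any reported side effect. It contains no severity split, no time limit, no phone or page step and no emergency referral.

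2. **The participant's own call (VI.D.i).** Participants are told to call both the study staff and the care team. This is a genuine second channel to the clinicians. It does not govern what staff do with a report they receive, and a participant who is confused or has just had a seizure may not make a second call.

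3. **The call/page route (opening of VI.D).** It is optional and is for medication questions. It leads to two study contacts who are not described as the participant's care team. In VI.D.i such contacts are available for the provider to consult, and the decision stays with the provider. The route helps, but it does not require staff to reach the treating clinician.

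4. **The drug recommendation (VI.D.i).** Here staff communicate with the participant's "provider in clinic and/or send a message through the EMR". Direct contact with the provider is therefore already an accepted channel at UAB, though for a different purpose.

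5. **The suicidal-ideation pager alert (section I, exclusion criterion 2).** It is triggered by a questionnaire answer, not by what a participant tells staff about a drug. The criterion excludes only the most frequent response on the PHQ-9 item, so a participant with less frequent ideation can be enrolled.

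6. **The Appendix 5 scripts.** They cover drug recommendations only.

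7. **Algorithm 2 (Appendix 1).** The figure is not visible in the text available, but VI.D.i describes its use as choosing which drug to recommend.

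None of items 2 to 7 changes item 1. The message is the only stated staff step for passing a reported side effect to the care team.

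Which Appendix 2 entries need direct contact is a clinical judgement. Seven are hard to dispute:

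| Drug | Entries | Count |
|---|---|---|
| Acamprosate | chest pain; thoughts or acts of self-harm | 2 |
| Disulfiram | allergic reaction or swelling; shortness of breath; seizure | 3 |
| Naltrexone | confusion; hallucinations | 2 |
| Total | 2 + 3 + 2 | 7 |

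Four more are plausible and need a clinical decision: yellowing of the skin or eyes, dark urine, fast heartbeat, and symptoms of depression. The count shows what a trigger list would contain. It says nothing about how often these effects occur.

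**The case against.** The strongest reply is that the sentence sets a default channel and forbids nothing. Staff who hear of a seizure would presumably do more than send a message, and emergency response is often left to clinic procedure. Such a procedure may exist, although this section cites none. Harm also depends on how messages are handled: if they are always read at once, the amendment adds little. Participants are told to call the care team in any case, and a serious effect of a study-recommended drug readily prompts a medication question to the study contacts.

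Much of this stands. It lowers the risk and keeps the point at the level of an improvement. It does not remove the point, because the protocol fixes one channel and following it exactly satisfies the protocol even for an urgent event.

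Three stronger readings are tempting, and the document supports none of them:

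- **Cerner is the only way a side effect can reach the care team.** The participant's own call is a second way.
- **Urgent reports will wait overnight or over a weekend.** Nothing is said about when calls are made, how soon messages are read or what cover exists, so no delay can be calculated.
- **Exposure can be read from the 259 participants planned at UAB (section I), or impact from the share of Appendix 2 entries that look urgent.** The number prescribed a drug is not given, and a share of list entries is not a share of events or patients.

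It would also be unfair to set the two channels for drug recommendations against the one for side effects as a like-for-like comparison. A recommendation can follow a clinic visit with the provider at hand, whereas side effects are sought by phone.

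**Conclusion.** The point holds in a limited form. At UAB the stated staff step for a reported side effect is a Cerner message whatever the severity, although the protocol's own drug list names effects that may be urgent. This is a stated rule that fits urgent events badly; it does not contradict other text.

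The size cannot be given. Events are likely to be few, the affected group is only those UAB participants who are prescribed a drug, and their number is unknown. The conclusion assumes that messages may not always be read at once and that staff may act on the written rule alone. It is worth acting on because the change is cheap and the consequence of a missed urgent report could be severe.

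**What to change.** Replace the relay sentence in VI.D.i with wording such as:

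> *If the participant reports an effect listed as more serious in Appendix 2 that may be urgent (at minimum thoughts or acts of self-harm, chest pain, seizure, allergic reaction or swelling, shortness of breath, confusion or hallucinations; clinical leads to confirm others such as yellowing of skin or eyes, dark urine, fast heartbeat or symptoms of depression), study staff/PCC contact the treating or covering clinician directly by phone, page or in person when it is reported, and also record it in the Cerner message center. Other side effects are sent through the Cerner message center as now.*

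The amendment should not say that a message is sufficient for all other effects. That would endorse message-only handling of possible jaundice, dark urine, fast heartbeat and depressive symptoms, which the current text does not do.

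The cost is one amended sentence, a clinical decision on the trigger list, an identified covering clinician, brief retraining and a few extra calls or pages. No extra staff are needed. Limiting the trigger to effects that may be urgent keeps complaints such as tiredness or appetite change from generating calls.
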